8.2 Laboratory Evaluations

- Serum chemistries including creatinine and electrolytes, GFR estimations (eGFR)
- Glucose and hemoglobin A1C
- Urine protein and urine albumin quantitative, urine creatinine and urine protein dipstick/with specific gravity
- Microalbumin/creatinine ratio and protein/creatinine ratio in urine
- Lipids.

8.3 Special Measures

- Health related quality of life and physical and emotional well-being from surveys to a small subset of participants.
- Primary care practitioner satisfaction with model of care for coexistent CKD, diabetes and hypertension

8.4 Special Measures

- All-cause hospitalizations
- Disease-specific hospitalizations for CKD, diabetes and hypertension: cardiovascular complications, heart failure, volume overload, hypertension, acute coronary syndrome, myocardial infarction, coronary/peripheral revascularization, stroke, limb ischemia/amputations, acute kidney injury, hyperkalemia, electrolyte disturbances, uncontrolled diabetes, hypoglycemia, diabetes complications, medication errors and drug toxicity, infections
- 30-day disease-specific readmissions (for patients with an index hospitalization)
- Emergency room visits
- Cardiovascular events
- Deaths

8.5 Sub-Study 1

Yield of Pharmacist Medication Reviews and Clinician Acceptance of Pharmacist Recommendations for Enrolled Patients at ProHealth

Background

ProHealth Physicians is an intervention site for a large, multisite, NIH-sponsored pragmatic clinical trial (“Improving Chronic Disease Management with PIECES”) which offers virtual pharmacist support for clinicians in the care of patients with the disease triad of chronic kidney disease (CKD), type 2 diabetes mellitus (DM), and hypertension (HTN). To date, our pharmacist has conducted over 300 medication reviews for these patients. Reviews assess: a) recommended practices in CKD (e.g. use of ACEi/ARB and statins), b) glycemic and blood pressure control, and, c) medication safety, which includes avoidance of nephrotoxic agents and renal dosing. The pharmacist makes patient-centered recommendations to clinicians to optimize and improve safety of regimens. Reviews and recommendations are entered as a Clinical Pharmacist Note in the electronic health record prior to primary care appointments. The pharmacist communicates electronically with clinicians for salient issues.

Objectives

The primary objectives of the proposed sub-study are to characterize a) medication-related problems (MRPs), and b) pharmacist recommendations among outpatients over 65 years old with chronic kidney disease, diabetes, and hypertension. A secondary objective is to evaluate the acceptance of virtual clinical pharmacist support in a large Primary Care Accountable Care Organization by evaluating clinician implementation of a pharmacist’s medication recommendations.

Methods

In this retrospective cohort study of 200 patients, medication-related problems and recommendations will be extracted from Clinical Pharmacist notes dated January 2017-May 2017 within the EHR.

Medication-related-problems and pharmacist recommendations will be classified as follows:

Category	Medication-related problem	Pharmacist recommendation
I. Safety	1. Contradiction 2. High dose 3. Adverse Drug Event (ADE) 4. Drug interaction 5. High risk medication (e.g. Beers List, anticholinergics)	a. Discontinue b. Decrease dose c. Renal dose adjustment d. Lab test / monitoring
II. Appropriateness	1. Needs additional medication 2. Unnecessary medication	a. Start medication b. Discontinue
III. Effectiveness	1. Ineffective 2. Low dose	a. Increase dose b. Alternative medication

This classification is based on a well-established taxonomy of MRPs. It was adapted to align with the focus of our medication reviews and patient population. Medication names and dosages will be collected to identify drug classes and specific medicines associated with MRPs.

Clinician acceptance of medication recommendations will be evaluated by review of medication profiles and Primary Care notes within one month after the timestamp of the Clinical Pharmacist Note.

Variables for the primary objective include: number of medication reviews, baseline patient characteristics (age, gender, mean eGFR and A1c, number of medications), number of medication related problems, and classification of MRPs and associated medicines. Variables for the secondary objective include number of medication recommendations accepted by primary care clinicians and acceptance rate.

Data Sources

Data will be extracted from the electronic health record; no patients will be contacted.

- *Demographics* – patient age, gender
- *Clinical Pharmacist notes* – MRPs, recommendations
- *Primary Care progress notes* – acknowledgment of pharmacist recommendations, documentation of medication changes
- *Medication profile* – medication and dose, medication changes
- *Laboratory results* – serum creatinine, eGFR, A1c, lipids, urine microalbumin, LFTs
- *Vitals* – blood pressure, heart rate

Impact

This study is important to identify common medication-related problems among these vulnerable patients with the disease triad of chronic kidney disease, diabetes, and hypertension. Results have potential to improve decision support for clinicians at the point of prescribing. This work also highlights the feasibility and value of adding virtual Clinical Pharmacist support for primary care teams in a large primary care-based Accountable Care Organization.

8.5 Substudy 2: Testing Computable Definitions of Acute Kidney Injury (AKI) in the ICD-Pieces Clinical Trial

Acute kidney injury (AKI) refers to an abrupt decrease in kidney function, resulting in the retention of waste products and in the dysregulation of electrolytes and extracellular volume¹. In the United States, about 300,000 people die from AKI each year, and the presence of AKI increases the length of a patient's hospital stay by 3.5 days.² Furthermore, it is recognized that there is an association between AKI and chronic kidney disease (CKD) and end-stage renal disease (ESRD).³ There is evidence of marked variation in the management of AKI, which is, to a large extent, due to a lack of awareness and an absence of standards for prevention, early recognition, and intervention. Emerging data point to an urgent need to change the treatment paradigm of CKD and other AKI risk factors by educating practitioners on how to prevent AKI (including the treatment of CKD), and modify its course with modalities and treatments that can improve outcomes.

Defined criteria to document AKI for research criteria (KDIGO, RIFLE,AKIN) have been used in research studies and compared to billing diagnostic codes for identification of AKI. In two recent studies the use of billing codes to identify AKI had low sensitivity compared with current KDIGO consensus definition or modified KDIGO definition (not counting urine output decrease as a criterion).^{4,5} In one study of

~34,000 hospitalized patients only 17.2% (95% CI 13.2%-21.2%) of AKI cases that were identified using serum creatinine were also identified using AKI billing codes.⁴ In a more recent report using

electronic health records, the ICD-10 code corresponding to AKI (N17) was recorded in 30% of the cases documented by a laboratory based approach to find Hospital Associated-AKI identified in a reported study.⁵ Furthermore, in a mini-sentinel pilot project sponsored by the US Food and Drug Administration (FDA) to improve electronic safety surveillance, the positive predictive values of ICD-9 diagnoses in identifying AKI ranged from 48%-84% at best.⁶

Improved standardized approaches to detect AKI in clinical trial adverse event reporting would improve safety monitoring and build the evidence base for defining subtypes of AKI in current studies and for future biomarker and precision medicine initiatives. We propose an additional substudy of the incidence of laboratory-defined AKI compared to administrative coding as an extension research question for the current ICD-Pieces pragmatic clinical trial. The ICD-Pieces study is focused mostly on capturing outpatient events. It is notable that 1/3 of AKI cases in a large epidemiological study were community acquired.⁷

Specific Aim 1:

Test the performance of laboratory based criteria for AKI compared to coded ICD-10 documentation of AKI in the outcomes data set of the ICD Pieces trial -UH3DK104655

As the ICD-Pieces trial will be following AKI as a subset of inpatient hospitalizations captured as part of the primary endpoint of the one-year unplanned hospitalization rate, a natural data set will be available to test for concordance of the laboratory only- based definition of AKI compared to ICD- 10 code documentation within a well- defined cohort with established baseline eGFR. AKI will be defined using KDIGO laboratory criteria. Although routine collection of information of urine output is not part of the trial, laboratory based data will be available along with the hospitalization data will be available for a section of the clinical sites including the North Texas VA hospital system, Parkland Health & Hospital System, and Texas Health Physicians Group of Texas Health Resources. This would demonstrate the feasibility of improved monitoring for adverse events, specifically AKI, in a large cluster randomized pragmatic clinical trial of patients with chronic kidney disease.

Specific Aim 2:

Document modern mappings of AKI based on the KDIGO criteria to current LOINC and SNOMED-CT Ontologies

8.7 Substudy 3: Understanding Decisions to Opt-Out of Pragmatic Clinical Trials

[name], MPH, MA

[name]

[name]

1. Abstract

Patients may sometimes be given the option to opt-out of pragmatic clinical research, which may mean not receiving a particular intervention based upon a study protocol or not having their data used for analyses. Yet, there is minimal information available about the reasons why patients opt-out, which may prove to be very useful in assessing the ethical, scientific, and practical aspects of pragmatic clinical trials. This project involves pilot testing a short survey instrument among patients who opt-out of ICD-PIECES, a pragmatic clinical trial currently being fielded to develop a preliminary understanding of reasons for opting-out as well as assemble a cohort of patients who may be interviewed in a possible qualitative interview study in the future.

2. Objectives

- a. To pilot test a short survey instrument regarding reasons for opting-out of pragmatic clinical trials.
- b. To develop a preliminary understanding of reasons for opting-out of ICD-PIECES, a pragmatic clinical trial currently enrolling participants.
- c. To obtain permission from patients who opt-out of ICD-PIECES for a possible in-depth interview regarding decisions related to opting-out that may be designed and conducted in the future.

3. Background

Pragmatic clinical trials and comparative effectiveness research are becoming increasing commonplace as a means of generating real-world information to guide medical decision making among patients, clinicians, payers and other stakeholders. This type of research typically poses minimal incremental risks to those involved and may be done without an explicit informed consent process. However, in such trials patients may be given the option to opt-out of the research, which may mean not receiving a particular intervention based upon a study protocol or not having their data used for analyses. Yet, there is minimal information available about the reasons why patients opt-out of pragmatic research, which may prove to very useful in assessing the ethical, scientific, and practical aspects of pragmatic clinical trials. Accordingly, the proposed research will pilot test a short survey instrument among patients who opt-out of ICD-PIECES, a pragmatic clinical trial currently being fielded. The estimated opt-out rate in ICD-PIECES is currently 1.5% of those approached.

4. Study Procedures

- a. Study design. Patients who opt-out of ICD-PIECES will be approached by the ICD-PIECES study coordinator immediately following their decision to opt-out and ask them if they would be willing to answer some questions about their decision. Answering these questions will be considered to indicate consent. The information will be captured on a form that will include only basic demographic and site information unless the patient voluntarily provides permission to be contacted. Primary data will be retained by the ICD-PIECES study team. Aggregate information will be provided without any patient identifiers to the study team at the NIH Collaboratory Coordinating Center (Drs. [name] and [name]).
- b. Study duration and number of study visits. The study will take 5-15 minutes at a single encounter.

5. Inclusion/Exclusion Criteria.

- a. Adult, competent patients who opt-out of ICD-PIECES
- b. Willing and able to answer questions related to their decision to opt-out
- c. Able to converse in English

6. Sample Size: 10-15 patients

7. Study Statistics

Data will be analyzed using standard descriptive statistics. We will endeavor to continue to enroll patients who opt-out of ICD-PIECES until enrollment for that study ceases.

8. Risks

There are no anticipated physical, financial or social risks for participating. Patients may feel uncomfortable discussing their reasons for opting-out. If this occurs, the survey can be stopped. If any unanticipated problems occur, the PI will be notified immediately and intervene as appropriate.

9. Benefits

There are no anticipated benefits to the participants. The information learned in this study should help assess and perhaps improve future pragmatic clinical trials and those who might participate in them.

10. Payment and Remuneration

None.

9 Assessment of Safety

9.1 Specification of Safety Parameters

Adverse safety events will be captured and monitored as part of the study. The primary outcome of this trial is all-cause hospitalizations for patients with a triad of CKD, diabetes and hypertension and all unplanned hospitalizations will be captured. The main secondary outcomes that will be captured in the study also include safety events including 30-day all cause readmissions (for those patients who have an index hospitalization), emergency room visits, cardiovascular events, deaths, and disease-specific hospitalizations. In this study disease-specific hospitalizations include all those hospitalizations for cardiovascular complications, congestive heart failure, volume overload, hypertension complications, acute coronary syndrome, myocardial infarction, coronary/peripheral revascularization, stroke, amputation/limb ischemia, uncontrolled diabetes, hypoglycemia, diabetes complications, acute kidney injury, hyperkalemia, electrolyte disturbances, medication errors, drug toxicity, and infections.

In this study the control group will receive standard of care. The intervention group will receive interventions that are already accepted as best practices. Primary care providers will make ultimate decisions regarding implementation of any of the interventions for both groups. In addition to the study outcome measures detailed above the following events will be captured and reported (whether they lead to hospitalizations or not) as they could be related to potential study interventions: hypotension, syncope, hyperkalemia, electrolyte disturbances, angioedema, hypoglycemia, rhabdomyolysis, myositis, drug toxicity, pregnancy while treated with ACEI or ARB, acute kidney injury, reductions in eGFR 50% or higher, or initiation of dialysis.

The study will monitor for any malfunctions on the decision support software system and SFTP used for data transmission to and from electronic health records of the study sites for Parkland, THR, ProHealth and VA of North Texas. There will also be monitoring for adherence to Manual of Procedure interventions including identification and enrollment of eligible patients, activation of study protocols and recommended follow up.

9.2 Methods and Timing for Assessing, Recording and Analyzing Safety Parameters

9.2.1 Adverse Events

The study outcomes and adverse/safety events detailed in Section 9.1 will be captured directly from the electronic health records of the participating healthcare systems, DFW Hospital Council and internal databases and event tracking forms from ProHealth and VA of North Texas as previously described. In this pragmatic trial capture of unsolicited events can occur in most instances from the electronic health records and databases. As noted above there will be confirmation for solicited adverse event including hospitalizations for patients from the VA of North Texas who may be seen in other institutions in Dallas/Fort Worth.

Adverse events will be collected throughout the entire participation of subjects in the study (12 months from enrollment to completion of the study participations for each subject). The study coordinating team will review adverse events to determine relatedness to study interventions and to grade severity as needed.

Adverse events will be classified as severe or mild/moderate. For the purposes of this study severe adverse events will include those leading to death, hospitalizations, or permanent disability/incapacity. Other safety events will be classified as mild/moderate. As the study relies heavily on event capture via the electronic health records it may not be possible in all instances to accurately differentiate between mild and/or moderate severity within the context of this pragmatic trial.

The study team will make determinations on whether serious adverse events are possibly/likely related to study interventions.

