9.2.3 Serious Adverse Events

Hospitalizations and deaths are serious events in this study. It should be noted that these adverse events classified as serious are already primary and secondary outcomes for this study (hospitalizations and deaths). Other serious events are those leading to incapacity and/or permanent disability and will also be captured as noted above.

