Fig. 1 Modulation of the intensiveness of glucose lowering in type 2 diabetes. Depiction of patient and disease factors that may be used by the practitioner to determine optimal HbA_{1c} targets in patients with type 2 diabetes. Greater concerns regarding a particular domain are represented by increasing height of the corresponding ramp. Thus, characteristics/predicaments toward the left justify more stringent efforts to lower HbA_{1c} , whereas those toward the right suggest (indeed, sometimes mandate) less stringent efforts. Where possible, such decisions should be made with the patient, reflecting his or her preferences, needs and values. This 'scale' is not designed to be applied rigidly but to be used as a broad construct to guide clinical decision-making. Based on an original figure by Ismail-Beigi et al [59]. ^a $\text{HbA}_{1c} 7\% = 53 \text{ mmol/mol}$

Protocol Figure 1. From Inzucchi SE et al. *Diabetologia* (2015) 58:434

The decision about what glucose control target to aim for in a given patient at a given time must take into account multiple factors that cannot be fully protocolized. *In striving to reduce the long-term risks of microvascular complications, it is important to remember that hypoglycemia, if severe and prolonged, may result in seizure, coma and death in the short-term.* Even mild hypoglycemia in someone driving a motor vehicle, for example, may result in significant harm to the patient and to others. The elderly are particularly at risk for falls resulting from hypoglycemia.

Monitoring Glucose Control: the Hemoglobin A1C (A1C)

Methods for monitoring glucose control include self-monitoring with glucose meters, continuous glucose monitors, and the hemoglobin A1C. For type 2 diabetes in non-insulin treated patients, the most pragmatic basis for making changes in therapy is the A1C, because it integrates glucose control over 2-3 months. Some caveats are necessary to recognize. First, A1C measurements may be falsely reduced in cases of shortened RBC lifespan, blood transfusions and hemolysis. Second, renal dysfunction and/or dialysis may complicate the relationship between A1C and glucose levels, so it is important to examine the patient's blood glucose logbook to assess glucose control by an independent method. In general, the A1C should be measured twice yearly in patients who are at goal and every 3 months in those who are adjusting their therapeutic regimen.

Hypoglycemia and the Rule of 15

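### Severity and seriousness are defined without a life-threatening criterion, so a life-threatening event released from the emergency room without an overnight stay is graded mild/moderate and non-serious

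*Combined protocol and SAP*

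**What the plan says.** Section 9.2.1 sets up two grades: "Adverse events will be classified as severe or mild/moderate". It then states that "severe adverse events will include those leading to death, hospitalizations, or permanent disability/incapacity", and continues: "Other safety events will be classified as mild/moderate". The same section has the coordinating team grade severity where needed, and warns that record-based capture may not separate mild from moderate. It gives no further grading criterion.

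Section 9.2.3 defines seriousness. It says "Hospitalizations and deaths are serious events in this study", and adds: "Other serious events are those leading to incapacity and/or permanent disability".

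Section 9.1 lists events to be collected whether or not the patient is admitted, because they could be related to what the intervention promotes. Hypoglycemia, angioedema, hyperkalemia, syncope and drug toxicity are on the list, which ends with "pregnancy while treated with ACEI or ARB, acute kidney injury, reductions in eGFR 50% or higher, or initiation of dialysis". Emergency room visits are a separate secondary outcome (section 3.2.2). Section 3.2.1 counts inpatient stays and overnight observation as hospitalization for the primary outcome.

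**The concern.** The rule reads severity from what happened to the patient afterwards, chiefly whether a bed was used, and makes no provision for how dangerous the event was. The protocol itself recognizes that a listed event can be acutely dangerous. Appendix II warns that "hypoglycemia, if severe and prolonged, may result in seizure, coma and death in the short-term". An episode of that kind that is reversed in the emergency room and discharged satisfies none of the routes to severe.

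What is at stake is the meaning of any table of severe or serious events. Such a table would leave out life-threatening events that did not end in admission, and a reader would take the mild/moderate column to contain nothing of that kind. The closing sentence of section 9.2.1 also ties one relatedness determination to serious events, so the omitted events fall outside that particular step.

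**Working it through.** The plan gives no figure on this point and no arithmetic applies. The check is to apply the written rule to event records and then look for any other provision that would change the result.

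**Inputs**
- Routes to severe (9.2.1): death, hospitalization, permanent disability/incapacity.
- Residual class (9.2.1): every other safety event is mild/moderate.
- Routes to serious (9.2.3): hospitalization, death, incapacity and/or permanent disability.
- Hospitalization (3.2.1): inpatient stay or overnight observation. I assume that 9.2.1 and 9.2.3 use the word in the same sense; they do not say so.

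**Rule applied to four illustrative records**, each with survival and no lasting disability:

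| Record | Meets a route? | Grade (9.2.1) | Serious (9.2.3)? |
|---|---|---|---|
| Hypoglycemia with seizure, treated in the emergency room, home the same day | No | Mild/moderate | No |
| The same event, kept overnight under observation | Yes, hospitalization | Severe | Yes |
| Angioedema with airway compromise, treated and released the same day | No | Mild/moderate | No |
| Brief hypotension, assessed and released the same day | No | Mild/moderate | No |

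The first two rows are the same clinical event, and only the overnight stay separates the grades. The fourth row shows that not every release is misgraded: an event of low intensity ends up where it belongs.

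**Is there a rescue elsewhere?**
- The verb in the severe definition could be read as open-ended, but the next sentence assigns everything else to mild/moderate and so closes the list.
- The team's option to grade as needed comes with no criterion for moving an event up.
- The caveat about limited record detail concerns mild versus moderate, not severe.
- Section 9.2.3 words its last route slightly differently, and incapacity is undefined. If temporary incapacity counted, a seizure might be called serious under 9.2.3, but it would still not be severe under 9.2.1, which speaks of a permanent state. The table takes incapacity as lasting.
- Elsewhere in the documents, life-threatening appears only in Appendix II, as a description of malignancy as a comorbidity.

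No provision changes rows one and three.

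**The case against.** The strongest reply is that no stated decision depends on the grade. Section 2.3 has the listed events reviewed monthly and reported quarterly to the DSMB with no severity filter, and section 9.3 sends adverse events to the DSMB quarterly. Section 9.2.4 triggers case review on rising frequency or rate of safety events of any grade. The halting rules in 9.5 do not mention severity, and section 11.3 contains no severity-graded analysis. Relatedness review is also broader than the closing sentence of 9.2.1 suggests: an earlier sentence there, and section 9.2.2, cover adverse events generally. Manual review covers the first 100 subjects per healthcare site and at least 10 per system each quarter. All of this stands, and it confines the point to grading. It does not make the grade right, because none of these provisions changes the class into which the rule puts the event.

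Three stronger readings are tempting and are not supported.

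- **That the intervention arm is made to look safer.** A reader might infer this because the intervention aims to reduce admissions, and admission is the main route to severe. Differential misgrading would require the intervention to change whether the same event is admitted or released. The intervention is delivered in outpatient primary care, and nothing in the documents shows that it affects emergency-room disposition. Fewer admissions because fewer events occur is not misgrading. Section 2.3 describes the listed-event report as covering the intervention group, so no written between-arm comparison of severity is identified either.
- **That the share of events treated and released equals the share misgraded.** Many released events may be mild or moderate, as the fourth record shows. The relevant share is of events both life-threatening and released, and the documents give no basis for it.
- **That every listed event treated in an emergency room, or every pregnancy exposure to an ACEI or ARB, should become severe.** The first replaces one disposition proxy with another. The second is an event type that is already reported as such, not a level of intensity.

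**Conclusion.** The point holds as a defect in a written rule. Under sections 9.2.1 and 9.2.3 a life-threatening listed event that is treated in the emergency room and released without an overnight stay, with no death or lasting disability, is graded mild/moderate and non-serious. The underlying cause is that the sections merge severity, which is intensity, with seriousness, which is outcome, and omit the life-threatening case from both.

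The effect is limited to severity and seriousness tabulations and to the relatedness determination that names serious events. The number of events affected cannot be estimated from the documents. The conclusion rests on two readings: that hospitalization carries its primary-outcome meaning, so that overnight observation escapes the gap, and that incapacity in 9.2.3 means a lasting state. If overnight observation were not counted in 9.2.1, the gap would be wider. Sample size, type I error and the primary analysis are not affected.

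**What to change.** 1. In both 9.2.1 and 9.2.3, add to the severe/serious criteria: *life-threatening, regardless of admission*.
2. Reword the residual sentence in 9.2.1 so that mild/moderate is reserved for safety events that meet none of the criteria.
3. Use the emergency-room visit data already captured to flag section 9.1 events for the life-threatening check. The flag prompts the check; it does not set the grade.

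While the sections are open, align the two wordings of disability and incapacity, and state that hospitalization has its section 3.2.1 meaning.

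The cost is a wording change in the protocol and manual of procedures, a flag on existing data, and somewhat more events to review. The change concerns classification only and touches no treatment rule.
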